## 16.2 Anticipated Adverse Events

The following events are known potential adverse events from the C-Scan procedure. They will be reported as adverse events for the purposes of the study:

- Delayed C-Scan Capsule excretion
- Capsule retention
- Change in bowel habits
- A small amount of fresh blood in the stool
- Potential difficulty swallowing the capsule
- Abdominal discomfort during the passage of the capsule
- Abdominal pain, cramps
- Back pain
- Nausea
- Loss of appetite
- Soft/runny stool
- More than 2/day bowel movements
- Diarrhea
- Constipation
- Allergic reaction to the ingested contrast material
- Skin irritation caused by the stickers on back
- Impaired night sleep caused by the C-Scan track (recorder on the back)
- Excessive radiation exposure (> 200 [ uSv] microSivert) Note: This threshold was calculated as 2X the max body dose in a long, but normal, procedure: total transit time of 100 hours and with 4000 scanning pages, which is the maximum ever reached during a normal procedure.

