After the capsule is expelled, the data from the recorder is downloaded to an acquisition workstation. Later, the data is transferred to a processing workstation and analyzed to create a map of the colon. The current C-Scan system is designed to operate for up to 100 hours. The average radiation dose calculated from these procedures is 52 uSV (typical results from last study: StD 38, Min. 19, Max. 165 uSV) – this is equivalent to one chest X-ray radiation.

	Document Title	Clinical Investigational Plan For Study CL-SY-02-0096		
	Document No.	DOC001593	Revision	03

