### **13.10 C-Scan Analysis**

Upon return of the capsule to the investigational site, the capsule data will be downloaded from the "Track" and validated for completeness by the technical team. Next, the raw data will be transformed to 3D format ('reconstruction') by the View workstation and optionally, selected bookmarks will be prepared for the Viewers.

The files will be transferred to designated centralized reading center (may be located outside the United States) and reviewed by three trained medical reviewers for clinical analysis and preparation of procedure subject report. Each reviewer will generate a final report including 'per patient' recommendations.

	Document Title	Clinical Investigational Plan For Study CL-SY-02-0096		
	Document No.	DOC001593	Revision	03

Decision on presence/absence of polyps will be determined by majority.

C-Scan findings will be compared to the FIT results and to the study Optical Colonoscopy procedure.

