#### 15.1.3 Capsule Retention

There is a low risk of capsule retention, *i.e.*, no excretion of the capsule after more than 300 hours (defined as SAE). Delayed capsule excretion is defined as no excretion of the capsule after 100 hours (approximately 4 days). In some instances, intervention is required to remove the capsule. Intervention, based on the physician's decision and imaging of the capsules location may include: use of laxatives, non-soluble fiber supplements, removal by colonoscopy or surgery.

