#### **15.1.4 Low X-Ray Body dose**

In addition, the capsule emits low level X-Ray radiation for a few seconds each time it scans the colon. The major source of radiation dose is from Ta182, a byproduct contaminant.

The radiation may potentially cause damage to the colon or nearby organs. Based on calculations the radiation dose level is rather low: 100 times lower than CT Colonography or similar to the radiation your body absorbs while flying from Europe to New York (8 hour flight = 0.06 mSv).

Once the capsule is excreted, the risk of radiation is eliminated.

	Document Title	Clinical Investigational Plan For Study CL-SY-02-0096		
	Document No.	DOC001593	Revision	03

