## 16 ADVERSE EVENTS

Subjects will be carefully monitored for adverse events. Subjects will be guided to report if they feel any pain or discomfort during the trial. At each visit or phone contact, subjects will be asked if they experienced any adverse reaction since the last visit.

Any adverse events with an onset following beginning of bowel preparation to colonoscopy procedure will not be collected. Colonoscopy related adverse events are not part of the study, are considered standard of care and will not be reported.

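### A body dose above 200 uSv is a reportable adverse event, but no step in the written plan estimates any subject's dose, so a count of zero could not be told apart from no measurement.

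*Combined protocol and SAP*

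**What the plan says.** Section 16.2 lists the known potential adverse events of the procedure and states of them: "They will be reported as adverse events for the purposes of the study". One entry is "Excessive radiation exposure (> 200 [ uSv] microSivert) Note: This threshold was calculated as 2X the max body dose in a long, but normal, procedure". The note goes on to describe that reference procedure as a transit of 100 hours with 4000 scanning pages. Section 16.3 adds that all anticipated and unanticipated adverse events will be collected and reported.

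On finding events, section 16 says: "At each visit or phone contact, subjects will be asked if they experienced any adverse reaction since the last visit". Sections 13.6.4, 13.7.2 and 16.4.1 likewise rely on calls and questions to the subject. Section 15.1.3.1 describes a Track fault indication and defines a safety malfunction as a risk of higher than usual radiation exposure. It leads to a clinic visit, an X-ray if the capsule is still in place, and removal.

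On processing, section 13.10 says "the capsule data will be downloaded from the 'Track' and validated for completeness by the technical team". Reconstruction and reading for polyps follow. Section 13.2 lists the raw procedure data among the items kept.

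For the last study, section 7.2 reports: "The average radiation dose calculated from these procedures is 52 uSV", with SD 38, minimum 19 and maximum 165 uSv. Section 8.1 lists a body dose well above the typical 50 uSv among that study's adverse events.

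Section 14.1.3 removes capsule failures, Track failures and noncompliant subjects from the statistical analysis.

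**The concern.** This adverse event is a number crossing a limit. A subject cannot feel it or report it, and the severity grades in section 16.3.1, which are worded in terms of signs and symptoms, do not describe it. It can be found only if someone calculates the dose, and the written steps never say that anyone does.

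Safety is the only primary objective, and radiation is the hazard that sets this capsule apart from an ordinary endoscopy capsule. If the report shows no exposure above 200 uSv, the reader needs to know whether 45 doses were calculated and all fell below the limit, or whether none was calculated. There would also be no dose distribution to set beside that of the last study.

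The exclusions in section 14.1.3 make this worse. A shield that does not retract is listed in section 16.1.4 as a malfunction with temporarily excessive radiation, so the subjects most likely to have a high dose are among those the analysis may drop.

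**Working it through.** **Step 1: the threshold.** Section 16.2 sets 200 uSv as twice the maximum dose of a long but normal procedure. That maximum is not printed, so it can only be solved for: 200 / 2 = 100 uSv. The one printed maximum is 165 uSv (section 7.2). It exceeds 100 uSv and is 165 / 200 = 83% of the threshold; twice it would be 330 uSv. The 165 uSv may come from a procedure not counted as normal, so this is not by itself a contradiction. It does show that recorded doses have come fairly close to the limit.

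**Step 2: search for a dose step.**

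| Place | Content | Dose estimated? |
|---|---|---|
| 10.3, 10.4 outcomes | Related serious events, compliance, satisfaction, transit, battery, performance | No |
| 5 and 13.1 schedules | No dose row | No |
| 13.2 documents | Raw data and C-Scan report | No dose item |
| 13.10 analysis | Completeness check, reconstruction, polyp reading | No |
| 14.1.1 to 14.1.5 statistics | Descriptive statistics in general terms | Dose not named |
| 15.1.3.1 scenarios | Fault indication, X-ray, removal | No dose, no link to 200 uSv |
| 16.3 event form items | Type, times, severity, relationship, outcome | No dose field |

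**Step 3: how likely is an event?** Inputs are mean 52 and SD 38 uSv (section 7.2), threshold 200 uSv (section 16.2) and n = 45 (section 14.1.1). The shape of the distribution is not given, so three are assumed. P(at least one) = 1 − (1 − p)^45.

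- Normal: z = (200 − 52) / 38 = 3.89, p = 0.00005. Expected 45p = 0.002; P(at least one) = 0.2%.
- Gamma: shape (52/38)² = 1.87, scale 38²/52 = 27.8, p = 0.0049. Expected 0.22; P(at least one) = 20%.
- Log-normal: σ² = ln(1 + (38/52)²) = 0.428, σ = 0.654, μ = ln 52 − 0.214 = 3.737, z = (ln 200 − 3.737) / 0.654 = 2.39, p = 0.0085. Expected 0.38; P(at least one) = 32%.

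The normal shape fits poorly. It puts P(z < −52/38 = −1.37) = 8.6% of doses below zero. The skewed shapes are more credible, but the documents do not settle the matter.

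**Step 4: what a zero would mean.** If all 45 doses were calculated and none exceeded 200 uSv, the one-sided 95% upper bound on the rate would be 1 − 0.05^(1/45) = 6.4%. If none was calculated, there is no bound. The plan as written does not say which case a reported zero would represent.

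**The case against.** The strongest reply is that the event need not go unseen. Section 16.3 requires anticipated events to be collected, section 13.2 keeps the raw data, and section 10.4 collects transit times and procedure duration. The last study produced calculated doses and recorded a high one as an adverse event. The case report forms and instructions for use are not part of the supplied text and the flow chart is not shown, so a dose field may exist elsewhere. This stands: a reader might infer that excessive exposures will be missed, and the documents do not support that. They support only that the written plan names no means of finding them.

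Asking subjects is also not the only route to an adverse event. Section 15.1.3 says "Delayed capsule excretion is defined as no excretion of the capsule after 100 hours (approximately 4 days"), and that is itself a listed event, with at least two calls a day until excretion. A long transit would therefore be noticed. This too stands, but what gets noticed is the elapsed time; no dose results from it.

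A reader might go further and calculate the hours at which a retained capsule crosses 200 uSv without any fault, since section 16.2 uses transit time and section 15.1.4 says "The major source of radiation dose is from Ta182, a byproduct contaminant". The documents do not give the share of dose that accrues with time, so no such figure can be supported. Nor do sections 15.1.3.1 and 16.2 contradict each other: the first is simply silent on dose.

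Finally, the primary outcome counts related serious adverse events, and exceeding 200 uSv is not defined as serious. This stands and limits the weight of the point.

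**Conclusion.** The point holds as a gap in ascertainment: a listed, reportable adverse event has no stated method by which anyone would establish that it occurred. The Track safety fault does not fill the gap, because it is not linked to 200 uSv and yields no dose.

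The consequence is limited to the adverse event tabulation and the missing dose summary. A reader might infer that the primary safety endpoint is compromised; it is not directly, unless such an event were judged serious. A reader might also infer that a zero count would prove nobody looked; the text supports only that the two explanations could not be separated.

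The chance of any event among 45 subjects is low to moderate, about 0.2% to 32%. That range assumes that doses in this study follow the last study's mean and SD and that one of the three shapes applies. The change is worth making, because safety is the sole primary objective and the cost is small.

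**What to change.** In section 13.10, require the sponsor's existing dose calculation for every subject from the retained procedure data. State its inputs (section 7.2 does not give them; section 16.2 names transit time and scanning pages), who performs it, when, and in which case report form field the result goes. State a conservative estimate to be used where Track data are lost.

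Record an adverse event whenever the calculated dose exceeds the 200 uSv already set in section 16.2, whether or not a fault was signalled.

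Report mean, SD, median, range and the count above 200 uSv for every subject who ingested a capsule. Say explicitly that the exclusions in section 14.1.3 do not apply to this summary.

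The cost is protocol wording and some derivation work. It should need no new subject procedure if the retained data hold the required inputs, which the sponsor should confirm. The downside is that events may be counted that would otherwise go unseen.

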## 16.3 Recording and Documentation of Adverse Events

All adverse events should be evaluated by the Investigator, and should be medically handled per investigator discretion. All adverse events shall be recorded in the subject's Adverse Event Case Report Form. The following data should be carefully documented:

- Subject's study ID/code
- Type of event
- Time of occurrence (i.e. date & time)
- Time of resolution (i.e. date & time)
- Severity degree (mild/moderate/severe/unknown)
- Relationship to study device (definitely/probably/possibly/probably-not/not-related)
- Measures taken (e.g. concomitant medication, hospitalization, etc.)
- Event outcome (unchanged/worsened/improved/resolved/unknown/death)

Adverse events will be assessed in terms of seriousness, duration, intensity and relationship to the study device and/or procedure. All anticipated and unanticipated adverse events will be collected and reported.

	Document Title	Clinical Investigational Plan For Study CL-SY-02-0096		
	Document No.	DOC001593	Revision	03

### **16.3.1 Severity**

The outcome of each adverse event will be observed and documented. Adverse events will be graded as follows:

- Mild: Sign or symptom, usually transient, requiring no special treatment and generally not interfering with usual activities.
- Moderate: Sign or symptom, which may be improve by simple therapeutic measures, may interfere with usual activities.
- Severe: Sign or symptom that is intense or debilitating and that interferes with usual activities. Recovery is usually aided by therapeutic measures and the discontinuation of the study device may be required.

### **16.3.2 Relationship**

The relationship of the adverse event to the study is defined as follows:

- Definitely: An adverse event was shown to be related to the study device.
- Probably: An adverse event has a strong temporal relationship to study device, and another etiology is unlikely or significantly less likely.
- Possibly: An adverse event has a strong temporal relationship to the study device, and an alternative etiology is equally or less likely compared to the potential relationship to the study.
- Probably not: An adverse event has little or no temporal relationship to the study device and/or a more likely alternative etiology exists.
- Unrelated: An adverse event has no temporal relationship to study device or has a much more likely alternative etiology.

## **16.4 Safety Reporting Procedures**

### **16.4.1 Adverse Events Reporting**

Subjects are encouraged to report any event to the study team and consult the PI for any change in their well-being. Subjects will be asked for any change in their medical condition during each study visit or phone call with the exception of Visit 2 for the standard of care Colonoscopy and the associated preparation procedure.

### **16.4.2 Serious Adverse Events Reporting**

Serious adverse events shall be reported to Check-Cap/Clinical Research Organization (CRO) in writing (using the Serious Adverse Events Form taken from the CRF) within 24 hours of the investigator's awareness of the event, and should be reported to the local Ethical Committee per their requirements.

### **16.4.3 Unanticipated Adverse Device Effect Reporting**

Unanticipated adverse device effects shall be reported to Check-Cap/CRO in writing (using the Serious Adverse Events Form taken from the CRF) within 24 hours of the investigator's awareness of the event.

Check-Cap/CRO will request additional information if needed and Check-Cap will report the event to the FDA within 10 working days of first notification of the event. The Investigator must notify their IRB of the event no later than 10 working days after learning of the vent.

	Document Title	Clinical Investigational Plan For Study CL-SY-02-0096		
	Document No.	DOC001593	Revision	03

## 17 DATA COLLECTION AND QUALITY CONTROL

### 17.1 Data Collection

Each investigative site will complete CRFs during the study. Each subject participating in the study must have all applicable CRFs accurately and diligently completed. It is the investigator responsibility to ensure by signature the completeness and accuracy of the CRFs.

Procedures report (e.g. optical colonoscopy report) and forms completed by the subjects (e.g. Diary) will be considered as source documents and provided to the sponsor de-identified. Copies of the CRFs may also be print out and used as source documents per site team convenience, as long as these are marked as source documents.

CRFs and any other study documents will not include any identifying details of the subjects, and all identifying details will be decoded to include study specific numeric code and subject initials.

Completed CRFs shall be monitored and verified against source documents, and signed by the investigator as a confirmation of accuracy and adequacy.

### 17.2 Data Monitoring

Monitoring will be conducted by the sponsor or designees per the study monitoring plan. Informed Consent Forms will be monitored for 100% adequacy and accuracy and study data will be monitored via a risk based approach outlined in the monitoring plan.

### 17.3 Data Archiving

All study documentation will be kept for a period of 2 years from study completion or termination, or the date which the records are no longer needed to support a premarket approval or De Novo classification application. Prior to discarding records, the investigative site should contact Check-Cap to receive clearance for proceeding or obtain alternative instructions

	Document Title	Clinical Investigational Plan For Study CL-SY-02-0096		
	Document No.	DOC001593	Revision	03

## **18 LABELING**

All equipment associated with the clinical study will be identified with visible markings stating:  
"CAUTION--Investigational device. Limited by Federal (or United States) law to investigational use"

## **19 DELIVERY, STORAGE AND DISPOSITION**

The C-Scan capsule and accessory kit will be shipped to the investigative site in advance of the procedure. Based upon the cadence of scheduled procedures, the site may be provided several units at a time to have inventory on hand.

All device and accessories must be tracked within the device accountability log and stored in a secure location available to only authorized study personnel. C-Scan should be kept in a dry location at room temperature.

At the end of the C-Scan procedure, a representative of the sponsor will collect the Kit, document and all unused material directly from the subject. C-Scan units returned from the subject will be shipped back to the sponsor.

## 20 ETHICAL AND LEGAL ASPECTS

### 20.1 Ethical Committee Review and Approval

Study protocol and applicable documents must be submitted to the Ethics Committee/IRB for approval prior to study commence. Documented approval will be obtained for all participating sites. When needed, study extension, amendment or renewal of the Ethical Committee approval must be obtained.

### 20.2 Ethical Conduct of the Study

The procedures set for the in this study protocol are designed to ensure adherence with Good Clinical Practices. This study must also comply with the local regulatory requirements.

Both the Investigator and the Sponsor are required to maintain study records, including regulatory approvals, as required by the applicable regulatory requirements.

The investigator must agree to the inspection of study related records by a regulatory authority or Check-Cap representatives and must allow direct access to source documents and any other study related documents.

### 20.3 Subject Information and Consent

Prior to the beginning of the trial, the investigator is responsible to obtain the Institutional Review Board approval of the written informed consent and any other written information provided to the subjects. Institutional Review Board approvals must be filed in the study records.

The process of obtaining informed consent must be in accordance with IRB approval, Good Clinical Practice, and local regulatory requirements. Written informed consent must be obtained prior to any study specific procedure.

### 20.4 Confidentiality

All subjects identifying records will be kept confidential. Subjects names will be kept confidential and all study records will include only subject study code and initials. If any identifying details (e.g. name, address, etc.) appears on any study related document, it must be redacted.

The subjects will be informed in writing (i.e. Informed consent), that representatives of the sponsor, CRO, Institutional Review Board or other regulatory authorities may inspect their medical records to verify the information collected and that all personal information made available for inspection will be handled in strict confidence and in accordance with local laws. Subjects will be informed in writing that any future publication will not include identifying information.

### 20.5 Insurance

The sponsor is responsible to provide insurance coverage for the clinical trial.

	Document Title	Clinical Investigational Plan For Study CL-SY-02-0096		
	Document No.	DOC001593	Revision	03

## 21 DISCLOSURE AND PUBLICATION OF INFORMATION

All proprietary information including; Check-Cap Ltd's operations, patent application, formulas, manufacturing processes, basic scientific data, and formulation information provided to the investigator or the methodologies used in this study, as well as proprietary information obtained during the course of the study are confidential and will remain the sole property of Check-Cap Ltd.

The investigator agrees not to disclose any proprietary information supplied by Check-Cap Ltd. in any way without prior written permission.

Individual subject data obtained during this study are confidential and will not be disclosed to third parties with the following exceptions:

1. When the data is needed by the subject's personal physician or other medical personnel responsible for the subject's welfare.
2. For data inspection and verification by Check-Cap Ltd. or designee, United States Food and Drug Administration, European Union or Israeli regulatory authority auditors or by the IRB.

Any manuscript or abstract produced by the investigators must be provided to Check-Cap LTD for review and approval at least 60 days prior to submission. Individual subject identity cannot be divulged in any publication.

	Document Title	Clinical Investigational Plan For Study CL-SY-02-0096		
	Document No.	DOC001593	Revision	03

## 23 APPENDICES:

- Subject's Satisfaction Questionnaire
- Subject's Satisfaction Questionnaire-Colonoscopy

CONFIDENTIAL

The information contained in this document is confidential and the sole property of "Check-Cap"  
Any reproduction in part or whole without the written permission of "Check-Cap" is prohibited

	Document Title	Clinical Investigational Plan For Study CL-SY-02-0096		
	Document No.	DOC001593	Revision	03

